8.2 Method of statistical analysis

The SAS9.13 statistical software will be used for statistical analysis. The effectiveness analysis will be performed in Full Analysis Set and Per-Protocol Set; the demographic analysis at baseline will be performed based on the Full Analysis Set; the safety evaluation will be performed in Safety Set. Descriptive summary statistics will be provided for all data. For classified variables, the frequency, percentage and 95% accurate binomial confidence interval of for point estimation shall be calculated; for continuous variables, the mean, median, interquartile range and 95% confidence interval for point estimation will be calculated. All statistical analyses are performed at the bilateral 0.05 significance level.

Kaplan Meier survival analysis shall be performed for all-cause mortality, aneurysm-related mortality, incidence of secondary intervention and other safety indicators during follow-up period.

A complete analysis of all safety evaluations will be provided, including the following analysis:

- Total number of serious adverse events (SAE)
- Total number of device-related adverse events
- Total number of device-related serious adverse events
- Total number of adverse events (AE)
- Number and percentage of subjects with serious adverse events
- Number and percentage of subjects with device related adverse events
- Number and percentage of subjects with device related serious adverse events
- Number and percentage of subjects with adverse events

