3.2 Project contents

The study is designed as a prospective, multi-centre, post-market, real-world observational registry study. Continuous enrollment is to be conducted for all subjects treated with Minos™ Abdominal Aortic Stent-Graft and Delivery System who meet the inclusion criteria and who voluntarily consent to participate in the study. An enrollment duration period of 24 months is expected for this project and initially, 200 subjects (170 in China and at least 30 in Europe) are to be enrolled. Patient follow up – including CT imaging - will be undertaken in accordance with the usual standard of care at participating sites, and is expected to occur at 30 days, 6 months, 12 months and 2-5 years post-procedure.

1. Primary endpoint

- Technical success rate at 12 months

2. Secondary endpoints

- Incidence of major adverse events at 30 days
- Immediate technical success rate
- Incidence of successful aneurysm treatment at 2-5 years
- All-cause mortality up to 5 years post-procedure
- Aortic aneurysm related mortality up to 5 years post-procedure
- Secondary intervention rates up to 5 years post-procedure
- Aneurysm diameter and variation in aneurysm diameter from 30 days to 5 years post-procedure
- Incidence of type I, III endoleaks from 30 days to 5 years post-procedure
- The incidence rate of stent migration, fracture, stenosis, occlusion and distortion from 30 days to 5 years post-procedure

3. Other endpoints: technical success rate of Hercules balloon and incidence of balloon rupture, where applicable.

In this study, immediate technical success rate, technical success rate at 12 months, secondary intervention rate, aneurysm diameter and variation in aneurysm diameter, and the incidence of type I and III endoleaks are used as efficacy indicators of the Minos™ Abdominal Aortic Stent-Graft and Delivery System. The incidence of 30-day major adverse events, all-cause mortality, aneurysm related mortality, stent migration, stent fracture, stenosis, occlusion and distortion are used as safety indicators of the Minos™ Abdominal Aortic Stent-Graft and Delivery System.

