7.2 Study Process

1. Case registration: The Internet registration system will be utilized to register all eligible patients who have been treated with Minos Abdominal Aortic Stent-Graft and Delivery System and who have voluntarily consent to participate in the study.
2. Signing the Informed Consent Form
3. Case screening: Cases are selected according to inclusion and exclusion criteria;
4. Case enrollment
5. Collecting the preoperative and intraoperative data
6. Postoperative follow-up: Imaging follow-up to be conducted in accordance with standard of care at participating sites, to include at 30 days, 6 months, 12 months and annually to 5 years after post-procedure. It is expected that all patients will complete this follow up schedule, but participants will not be excluded in the event that follow up is not completed.
7. Data analysis and summary: All relevant data will be collected and analysed from time to time as the study progress.

Flow chart of study:

Project	Visit1	Visit2	Visit3	Visit4	Visit5	Visit6	Visit (7-10)
Time points	Preoperative	Intraoperative	Discharge	30 days after surgery	6 months after surgery	12 months after surgery	2/3/4/5 years after surgery
Window period ³				±7d	±30d	±60d	±90d
Informed consent ¹	X						
Demographics	X						
Inclusion criteria	X						
Baseline / Disease history	X						
Physical examination	X						
Blood test ²	X		X				
CT	X			X ^{4, 5}	X ⁴	X ⁴	X ⁴
Record of operation process		X					
Evaluation of adverse event		X	X	X	X	X	X

Note:

1. The subjects shall complete the signing of the Informed Consent Form before enrollment into the study. This will ideally be prior to the treatment procedure. The absence of laboratory test and imaging examination shall not be considered as a protocol deviation.
2. Blood examination includes standard of care tests in the study site, likely full blood count and standard liver and kidney function tests.
3. CT images collected outside of the follow-up window after surgery will not be considered as a protocol deviation.
4. CT imaging may not be undertaken at all follow up points if it is not the treating institution's standard of care to do so. In such cases, alternative imaging can be recorded i.e. USS.

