8.5 Procedures for processing missing, unused, incorrect or unreasonable data

Statistical analysis will be undertaken in accordance with the corresponding standard operating procedure (SOP). Refer to the relevant documentation for details. Incorrect data will be identified and rectified during the data cleaning process prior to statistical analysis. Data relating to patients who have withdrawn from the study will be included in the final statistical analysis. Specific reasons for all patients who have withdrawn from the study will be described in the statistical report. Missing data relating to the study's primary endpoint caused by premature withdrawal will be imputed in accordance with the above-mentioned strategy for missing values. This imputation process will not be performed for missing data relating to any other endpoints.

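### Type I/III endoleak from 30 days to 5 years is not named for time-to-event analysis, so by default it gets a simple percentage with no stated denominator

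*Protocol*

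**What the plan says.** Protocol section 3.2 sets the secondary endpoint as "Incidence of type I, III endoleaks from 30 days to 5 years post-procedure". The same section states that "the incidence of type I and III endoleaks are used as efficacy indicators", and separately that "aneurysm related mortality, stent migration, stent fracture, stenosis, occlusion and distortion are used as safety indicators". Endoleak is not in the safety list.

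Section 8.2 assigns the methods. For categorical data: "For classified variables, the frequency, percentage and 95% accurate binomial confidence interval of for point estimation shall be calculated". For time-to-event data: "Kaplan Meier survival analysis shall be performed for all-cause mortality, aneurysm-related mortality, incidence of secondary intervention and other safety indicators during follow-up period". Effectiveness is analysed in the full analysis set and the per-protocol set. No denominator is given for any percentage.

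Four other places bear on the point:

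- Section 7.2, note 4 to the flow chart, lets CT be omitted where it is not local standard of care; other imaging, such as ultrasound, may be recorded. The same section says that "participants will not be excluded in the event that follow up is not completed".
- Section 8.5 keeps withdrawn subjects in the final analysis. After describing imputation for the primary endpoint it adds: "This imputation process will not be performed for missing data relating to any other endpoints".
- The endoleak definition in section 7.1.6 counts an untreated endoleak seen at several visits once per subject.
- Section 13.1 includes type I/III endoleak among device-related adverse events.

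**The concern.** Migration, fracture, stenosis, occlusion and distortion are safety indicators in 3.2 and so come under Kaplan-Meier in 8.2. Endoleak covers the same five years, is found by the same imaging and is lost to the same missed scans and deaths, yet it is left to a frequency and a binomial interval.

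A cumulative incidence over five years, with staggered loss of imaging and with deaths, is not in general estimated by a simple percentage, whichever fixed denominator is chosen. If the denominator is everyone in the set, a subject last imaged leak-free at 6 months counts the same as one imaged leak-free at 5 years, and poorer imaging then makes the device look better. If the denominator is those imaged at a given visit, the result describes that visit and not the period named in the endpoint. The protocol (section 4) says that the registry is there to observe medium- and long-term outcomes, so a 5-year figure of uncertain meaning matters, though it carries no hypothesis test.

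**Working it through.** The protocol gives no endoleak rate, no rate of loss of imaging and no precision target, so there is no planned figure to reproduce. The check has two parts.

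**Which method applies**

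| Event over follow-up | Class in 3.2 | Named in the 8.2 Kaplan-Meier sentence? |
|---|---|---|
| All-cause and aneurysm-related death | safety | yes, by name |
| Migration, fracture, stenosis, occlusion, distortion | safety | yes, through the closing phrase on other safety indicators |
| Secondary intervention | efficacy | yes, by name |
| Type I/III endoleak | efficacy | no |

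Secondary intervention shows that an efficacy event can be brought in by naming it. Endoleak was not named. Section 13.1 could bring it in as a safety event, but the summaries that 8.2 lists for device-related adverse events are again numbers and percentages.

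**What the denominator does**

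Inputs:

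- Death: 10/136 at 12 months in the earlier study (section 4), assumed constant over 5 years. m = -ln(1 - 10/136) = 0.0764 per year; survival at 5 years = exp(-5 × 0.0764) = 0.68.
- True cumulative incidence with death competing: F = 10% (assumption).
- Loss of imaging: c = 0.05, 0.10 or 0.15 per year (assumption). The share of survivors still imaged at 5 years, exp(-5c), is 78%, 61% and 47%.
- Period: T = 5 - 1/12 = 4.917 years. n = 200, with all in the analysis set.

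The expected share of the whole set with an observed endoleak, for a constant endoleak hazard h, is

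P(c) = h/(h + m + c) × [1 - exp(-(h + m + c)T)].

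Solving P(0) = 0.10 gives h = 0.0259 per year. Then:

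| c | h + m + c | P(c) | P(c)/F | Coverage of exact 95% interval, n = 200 |
|---|---|---|---|---|
| 0.05 | 0.1523 | 8.96% | 0.90 | 95% |
| 0.10 | 0.2023 | 8.06% | 0.81 | 89% |
| 0.15 | 0.2523 | 7.29% | 0.73 | 80% |

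Coverage is the binomial probability, at success rate P(c), that the Clopper-Pearson interval contains 10%.

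Sensitivity:

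- At F = 5% the ratios are nearly the same (0.89, 0.80, 0.73), but coverage is 97%, 96% and 93%. The relative bias hardly depends on the true rate; the under-coverage does.
- With the hazard four times higher in year 1, the ratios rise to 0.93, 0.87 and 0.81.
- A simulation without death, with endoleak found only at the scheduled visits (3,000 runs of 200, F = 10%), gave a crude 8.8% with 80% still imaged at 5 years and 6.9% with 50%. Kaplan-Meier gave 10.0% in both. The same formula without death gives 9.0% and 7.3%, so detection at visits makes the dilution slightly larger.

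Restricting the denominator does not recover the target either. Among subjects alive and imaged at 5 years, the share who ever had an endoleak is 1 - exp(-hT) = 1 - exp(-0.0259 × 4.917) = 11.9%, if endoleak affects neither death nor imaging. Kaplan-Meier with deaths censored aims at the same 11.9%, which is why death should be treated as a competing event.

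**The case against.** The strongest case against is that the protocol never states a whole-set denominator and never says that an unimaged subject counts as leak-free. This stands. The rule in 8.5 against imputing non-primary endpoints can fairly be read as leaving missing assessments out of the denominator, and keeping a subject in the study is not a rule for scoring an unseen endpoint. A reader might infer from 8.1, 8.2 and 8.5 that the dilution is built into the plan. The documents do not support that: it arises under one reading of an unstated denominator. Section 8.4 also plans analyses by time point, and percentages of those imaged at each visit would not be diluted in this way.

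It is equally tempting to say that endoleak is denied Kaplan-Meier because it is classed as efficacy. That does not hold, since 3.2 places "immediate technical success rate, technical success rate at 12 months, secondary intervention rate" in the same efficacy list and 8.2 still names secondary intervention. With 13.1 calling endoleak a device-related adverse event, it could also be read as one of the other safety indicators.

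It can further be said that denominators belong in a statistical analysis plan, which is not at hand. That is true of the denominator alone. But 8.2 itself allots estimators to endpoints, and this allotment leaves one 5-year event out and sits badly with 13.1. No fixed denominator turns a simple percentage into the incidence that 3.2 names. The once-only counting rule in 7.1.6 suggests that a cumulative count per subject is meant.

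**Conclusion.** The point holds in a limited form. As written, 8.2 leaves type I/III endoleak from 30 days to 5 years to a simple percentage with an exact binomial interval, while the comparable stent events get time-to-event analysis. Sections 3.2, 8.2 and 13.1 do not agree on whether endoleak is an efficacy or a safety matter.

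The size is conditional. If the whole set is the denominator and unimaged subjects count as leak-free, the figure is about 10% to 27% too low in relative terms at imaging loss of 5% to 15% per year with a constant hazard, and about 7% to 19% too low with a front-loaded hazard. This rests on assumed loss rates, on one-year mortality carried forward for five years, and on loss of imaging unrelated to endoleak. It does not show that the reported rate will be biased. The endpoint is secondary and descriptive, in a study without a formal hypothesis test, so the priority is moderate.

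**What to change.** In section 8.2:

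1. Name type I/III endoleak among the time-to-event endpoints. Report its cumulative incidence from 30 days to 5 years with death as a competing event (Aalen-Johansen), censoring each subject at the last imaging able to show an endoleak.
2. Give visit-specific percentages, with the number imaged at that visit as denominator.
3. Reconcile 3.2, 8.2 and 13.1, so that it is clear whether endoleak is an efficacy indicator, a safety indicator or both, and which analysis follows.

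The cost is a few sentences and one more analysis of data already collected. The reported incidence may be higher and less precise. The competing-risk estimate will also not be on quite the same scale as the Kaplan-Meier curves planned for the other events, and the report should say so. Limits remain: endoleak is seen only at imaging, so its time is interval-censored, and loss of imaging may be informative. The report should therefore show the number still under imaging at each time point.

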Pre-clinical testing was completed prior to CE marking and approval for use in the EU and a domestic pre-clinical investigation of the device in human patients was conducted following successful preclinical trials and testing. A total of 137 patients were enrolled, with an average age of 69.5 years. The 12-month clinical success rate was 89% (121 / 136), the rate of 30-day major adverse events was 1.5% (2/136), the 12-month all-cause

mortality was 7.4% (10 / 136), the aneurysm related mortality was 0.7% (1/136), and the safety and effectiveness have been verified. Therefore, the Minos™ Abdominal Aortic Stent-Graft and Delivery System has been authorized with the Registration Certificate for Medical Device of the People's Republic of China in March 2019, Certificate No.: GXZZ 20193130182. And was CE-Marked in September 2019, Certificate No.: M.2019.106.12584. On this basis, this post-market registry has been commenced to observe the medium and long-term clinical outcomes of Minos™ Abdominal Aortic Stent-Graft and Delivery System in the treatment of AAA in a real-world patient population.

References

- [1] 中华医学会外科学分会血管外科学组腹主动脉瘤诊断与治疗指南. 中国实用外科杂志, 2008, 28(11): 916-917.
- [2] YII M K. Epidemiology of abdominal aortic aneurysm in an Asian population. ANZ J Surg, 2003, 73(6): 393-395
- [4] Lederle F A , Freischlag JA , Kyriakides T C , et al. Long-term comparison of endovascular and open repair of abdominal aortic aneurysm. N Engl J Med, 2012, 367 (21): 1988-1997.
- [6] Barbanti M, Binder RK et al. Impact of low-profile sheaths on vascular complications during transfemoral transcatheter aortic valve replacement. EuroIntervention. 2013 Dec; 9(8):929-35.

5、 Product features, structural composition, working principle, mechanism of action and scope of study

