8.4 Criteria for termination of the study based on statistics

This study does not pre-establish interim analysis and the corresponding premature termination criteria, so this section is not applicable.

As a real-world study, the subjects will be followed up for 5 years. Periodic data statistical analysis is planned for 30 days, 6 months, 12 months, and 2-5 years post-procedure surgery. All statistical analyses shall be performed after the data have been collected, cleaned, and finally locked.

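### Section 8.2 applies Kaplan-Meier to 5-year endpoints that death precludes; with those deaths censored, the curves overstate real-world incidence

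*Protocol*

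**What the plan says.** Section 8.2 of the protocol fixes one estimator for several endpoints: "Kaplan Meier survival analysis shall be performed for all-cause mortality, aneurysm-related mortality, incidence of secondary intervention and other safety indicators during follow-up period". Section 3.2 shows what the last group contains: "stent migration, stent fracture, stenosis, occlusion and distortion are used as safety indicators".

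The horizon in section 3.2 is long: "Aortic aneurysm related mortality up to 5 years post-procedure", "Secondary intervention rates up to 5 years post-procedure" and "The incidence rate of stent migration, fracture, stenosis, occlusion and distortion from 30 days to 5 years post-procedure". Section 8.4 confirms that "the subjects will be followed up for 5 years".

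The only death rates in the protocol are in section 4 (Study background), for the earlier study of the device: 12-month all-cause "mortality was 7.4% (10 / 136), the aneurysm related mortality was 0.7% (1/136"), in patients "with an average age of 69.5 years".

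Two other provisions bear on the point. Section 8.2 also plans frequencies and percentages with exact binomial intervals for categorical variables. Section 7.1.6 has the Clinical Events Committee judge every death for its relation to the aneurysm, the device or the surgery. No section mentions competing risks or cumulative incidence, or says what happens to a subject who dies before the event of interest. Section 8.5 deals with withdrawal and missing data, not with death.

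**The concern.** Kaplan-Meier treats a censored subject as someone who could still have the event later. That is reasonable for a subject who has moved away. It is not reasonable for a subject who has died of something else, who can never have a reintervention, a stent occlusion or an aneurysm-related death. Censoring such deaths makes one minus Kaplan-Meier (1-KM) an estimate of risk in a hypothetical population in which nobody dies of other causes. It is never below the actual cumulative incidence, and it exceeds it once competing deaths precede events.

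The registry's stated aim is to describe outcomes in a real-world population over the medium and long term. The patients are elderly and, in the earlier study, 9 of the 10 deaths were not aneurysm-related. The gap between the two quantities grows with follow-up and does not shrink with sample size. Section 17 asks for results to be discussed against those of similar products, where an overstatement that comes from the method would count against the device.

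**Working it through.** **Inputs**
- Section 4: 12-month all-cause mortality 10/136 = 7.35% (stated as 7.4%); aneurysm-related mortality 1/136 = 0.74% (stated as 0.7%). Both stated figures reproduce.
- Sections 3.2 and 8.4: 5-year horizon.
- Assumptions, because the protocol gives no figure: constant hazards over 5 years, and a secondary intervention hazard of 0.03 per year, varied from 0.01 to 0.05.

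**Formulas.** For an event hazard h, a competing death hazard D and time t:
- 1-KM with deaths censored = 1 − exp(−h·t)
- cumulative incidence = h/(h+D) × [1 − exp(−(h+D)·t)]

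**How common is death?** The all-cause hazard is H = −ln(1 − 10/136) = 0.0764 per year. Mortality by 5 years is 1 − exp(−5 × 0.0764) = 31.7%.

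**Aneurysm-related mortality at 5 years.** h = −ln(1 − 1/136) = 0.00738; D = 0.0764 − 0.0074 = 0.0690.
- 1-KM = 1 − exp(−0.0369) = 3.62%
- cumulative incidence = (0.00738/0.0764) × 31.7% = 3.07%
- difference 0.56 points, ratio 1.18. Taking exactly one death in ten as aneurysm-related gives 3.75% against 3.17%, with the same ratio.

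**Secondary intervention at 5 years.** h = 0.03 (assumed); D = 0.0764.
- 1-KM = 1 − exp(−0.15) = 13.9%
- cumulative incidence = 0.03/0.1064 × [1 − exp(−0.532)] = 11.6%
- difference 2.3 points, ratio 1.20. For h from 0.01 to 0.05 the ratio stays at 1.19 to 1.20. The same arithmetic applies to a device event with the same hazard.

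**Sensitivity**

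| Scenario | 1-KM | Cumulative incidence | Ratio |
|---|---|---|---|
| Intervention, 5 years, annual mortality 3% (assumed) | 13.9% | 12.9% | 1.08 |
| Intervention, 5 years, annual mortality 5% (assumed) | 13.9% | 12.3% | 1.13 |
| Intervention, 12 months, mortality as in the earlier study | 2.96% | 2.85% | 1.04 |
| Intervention, same 5-year total hazard (0.15) with 60% of it in year 1, mortality as in the earlier study | 13.9% | 12.5% | 1.11 |
| Aneurysm-related death, whole risk within 30 days | 0.735% | 0.733% | 1.00 |

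**Against sampling error.** Approximate 95% half-widths at n = 200, 1.96 × √[p(1−p)/200], are 2.4 points at p = 3.1% and 4.4 points at p = 11.6%. In both cases the bias is smaller than the half-width.

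**The case against.** The strongest reply has four parts.

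First, section 8.2 does not say that deaths are censored or that 1-KM will be reported as incidence. Death could instead count as an event, giving event-free survival, and such rules are often left to the analysis plan. This stands in part: the bias is conditional on censoring. But the protocol itself names the estimator, in one sentence, for endpoints of different kinds. For aneurysm-related mortality, counting other deaths as events would turn the endpoint into all-cause mortality, so censoring is the natural reading.

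Second, risk net of unrelated death is a legitimate measure of device durability and may travel better between populations. This stands for migration, fracture, stenosis, occlusion and distortion as a supplementary quantity. It is weaker for aneurysm-related death, and it does not describe what happens to real patients.

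Third, the size is uncertain. The mortality input is one 12-month figure (exact 95% interval for 10/136: 3.6% to 13.1%), the aneurysm-related share rests on one death (exact interval for 1/136: 0.02% to 4.0%), and the intervention rate is assumed. All of this stands. It limits what can be said about size, not about direction.

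Fourth, the study is descriptive with no formal test, the bias lies within sampling error, and it makes the device look worse rather than better. This stands as a limit on severity. Sampling error is reported by an interval, however, while a one-directional bias is not.

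A reader might infer that all the registry's 5-year rates will be inflated. The documents do not support that: the crude percentages planned in the same section do not treat the dead as still at risk. With losses to follow-up, though, they do not replace a sound time-to-event estimate. A reader might also extend the point to endoleak. The Kaplan-Meier sentence does not name it, and section 3.2 classes type I and III endoleak as an efficacy indicator, so it is left out here.

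**Conclusion.** The point holds as a moderate one. Section 8.2 prescribes Kaplan-Meier for endpoints that death precludes and nowhere provides for death as a competing event. With those deaths censored, 1-KM overstates real-world incidence; the direction is certain.

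At 5 years the overstatement is up to about 18 to 20% in relative terms if the earlier study's 12-month mortality persists unchanged, and about 8 to 13% for secondary intervention if annual mortality is 3 to 5%. These are illustrations from extrapolated and assumed inputs, not forecasts, and early clustering of events would reduce them. All-cause mortality is correctly handled, and the 12-month primary endpoint is not in the Kaplan-Meier sentence. The change should be made because it concerns core long-term results and is cheap, not because the registry's conclusions hang on it.

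**What to change.** In section 8.2, and in the analysis plan that follows it:
- Keep Kaplan-Meier for all-cause mortality, and for event-free survival if that is wanted.
- For aneurysm-related mortality, report the Aalen-Johansen cumulative incidence with death from other causes as the competing event.
- For secondary intervention and for stent migration, fracture, stenosis, occlusion and distortion, report the Aalen-Johansen cumulative incidence with any death as the competing event.
- Give 95% confidence intervals at the planned annual time points (12 months and 2, 3, 4 and 5 years).
- If a Kaplan-Meier curve is kept as a durability measure for device events, label it as net risk with deaths censored and present it as a supplement.

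The cost is a change of wording, slightly more analysis work, and a check that the SAS version named in section 8.2 supports the estimator. No new data are needed, because the Clinical Events Committee already judges the cause of every death.
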